Intervention to Change Attributions that are Negative (ICAN): a New Approach to Reducing Anger and Aggression after Brain Injury

Study Protocol and Statistical Analyses Plan

Clinicaltrials.gov #: NCT03648476

Unique Protocol ID: 1806829789

Secondary IDs: 1R21HD094232-01

April 19,2021

STUDY PROTOCOL

Study Design. We will conduct a small, randomized waitlist controlled trial of the ICAN intervention to examine feasibility and acceptability (Aim 1); effect size estimates on perspective taking and hostile attributions (Aim 2); and anger and aggression (Aim 3) in participants with TBI.

Inclusion/Exclusion Criteria.

Inclusion Criteria

- History of complicated mild to severe TBI (injury due to an external physical force), with injury severity being defined *either by*¹ Glasgow Coma Score at time of injury (≤ 12), or post-traumatic amnesia (≥ 1 day), or loss of consciousness (≥ 30 minutes), or positive head CT scan consistent with TBI.
- At least 18 years of age or older;
- ≥ 1 year post-injury;
- Have adequate vision, hearing, and speech/ language skills to participate in assessments and group therapy (determined based on interaction with the participant at screening)
- Have adequate reading comprehension (due to the primary assessment involving written scenarios)
- Have abnormal scores on one or more of the below measures of negative attributions or perspective taking (determined at T0 screening):
 - Epps Intent: >4.8 , or
 - Epps Hostility: >4.2 , or
 - Epps composite score: >-0.2 , or
 - AIHQ Intent: >3.3 , or
 - IRI Perspective Taking: < 14.5 for men and < 15.5 for women
- Have above average aggression (>49 at telephone prescreening; >55 at T0 screening) on one of the Buss Perry Subscales.
- No anticipated medication changes for emotions/ behavior during length of study participation; medications for emotions/ behavior must be stable within last 30 days prior to consent at T0 (Screening)
- Have reliable mode of transportation

Exclusion criteria:

- Pre-morbid neurological disorders that could affect mood and cognition (e.g. stroke); does not include controlled seizures
- Progressive central nervous system disorders (e.g. dementia, Parkinson's)
- Developmental disability (e.g., autism, developmental delay);
- Major psychiatric disorders (e.g. schizophrenia, Borderline Personality Disorder);

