- Severe Depression and/or perceived risk to self or others (mental health resources will be provided and if suicide risk, approved suicide protocol will be utilized);
- Currently receiving active behavioral therapy for anger.
- On drug research study for irritability, anger, aggression

Note: Participants will not be excluded if they do not have caregiver.

Sample Size Calculation. Forty participants (20 per group) will be enrolled to allow for 20% dropout. Thirty-two participants (16 per group) are expected to finish the study. For Aim 1, feasibility and satisfaction percentages of 80%, a sample size of 30 will allow these proportions to be estimated to within 13% using one-sided 95% confidence intervals. For between group effect sizes for Aims 2 and 3, a sample size of 21 per group will detect an effect size of 0.9 standard deviations with 80% power using a two-sided t-test at a .05 level of significance. An ANCOVA model with pre/post correlation of 0.5 can reduce the sample size needed by 25% or to 16 per group. For within group effect sizes for Aims 2 and 3, 16 subjects will provide 80% power to detect a difference in means of .78 standard deviations using a two-sided paired t-test at the .05 level of significance.

Recruitment. The Rehabilitation Hospital of Indiana (RHI), an affiliate of Indiana University (where the PI and Co-I's have offices), will be a primary source of recruitment (see [name] LOS). IU/RHI is one of 16 nationally recognized Traumatic Brain Injury Model Systems (TBIMS) sites in the United States, making it a strong site for recruitment of this population. On average, RHI admits around 120 individuals with TBI annually; $>1,000$

individuals with TBI are seen in the RHI outpatient clinics. We will use 1) past RHI inpatients, 2) RHI Outpatient Clinic, 3) RHI Research Registry (n=295), and 4) IU/RHI TBIMS Database (>230 enrolled to date). We will recruit through letters sent by physicians to their patients, pre-clinic chart screening, clinician discussions with patients, flyers posted in RHI, recruitment videos shown around the facility, researchmatch.com and through The Rehabilitation Hospital of Indiana's Facebook page. Flyers will be distributed at TBI support groups and the Brain Injury Association of Indiana. RHI patient letters will be followed with a phone call to confirm receipt of the letter and inquire about interest in the study. See Pre-screen below.

Outcome Measures.

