Cognition/ Executive Functioning: We will assess executive functioning skills for attention, dis-inhibition and verbal fluency. The following tests were chosen based on findings from our preliminary study. Color-word interference (Stroop): Attention and dis-inhibition will be assessed with a commonly used color-word interference test that assesses skills such as basic color naming; word reading; and names of colors written in different color ink (participants must name the color of the ink, not read the words). Verbal Fluency: assesses word association fluency; we will examine letter fluency and category fluency. This test measures a person's ability to make verbal associations to letters and categories. Responses for verbal fluency will be audio recorded for data integrity.

Neurobehavioral Functioning: We will evaluate how participants' caregivers perceive the neurobehavioral functioning of our participants with TBI with the Frontal Systems Behavior Scale (FrSBe).^{18,19} It is a 46-item subjective questionnaire that measures apathy, dis-inhibition, and executive dysfunction with a 5-point Likert scale. The FrSBe has good reliability and validity^{18,19} and has been used in variety of clinical populations, including brain injury and Alzheimer's disease.²⁰

Table 1a. ICAN MEASURES AND TIMELINE (Subjects with TBI)

	T0 (screen)	T1	T2	T3 (WLC only)
Consent/ HIPPA*	X			
Demographics*; TBI History*; medication infor and therapy status*	X (inc)			
Med and therapy status update only*		X	X	WLC only
Discourse Comprehension Test*	X (inc)			
Epps stories (attribution and anger to hypothetical scenarios)	X (inc)		X	WLC only
AIHQ Scenarios	X (inc)	X**	X	WLC only
IRI Perspective Taking and Empathetic Concern*	X (inc)	X**	X	WLC only
Buss Perry Aggression*	X (inc)		X	WLC only
NIH Toolbox Anger Affect*		X	X	WLC only
TASIT (theory of mind)		X	X	WLC only
PHQ9 (Depression)*	X (inc)		X	WLC only
GAD7 (anxiety)*		X	X	WLC only
TAS-20 (alexithymia)*		X	X	WLC only
DERS (emotion regulation)*		X	X	WLC only
COWAT verbal fluency (cog f)*	X			
Color word interference (Stroop) (cog f)	X			

Patient Global Impression of Change in Anger and Aggression*			X	WLC only
Patient Global Impression of Change in Empathy/ Perspective Taking*			X	WLC only
Client Satisfaction Questionnaire 8 (CSQ-8)*			ICAN only	WLC only
Post-Treatment Qualitative Interview*			ICAN only	WLC only
RA opinion of group allocation			X	

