* May be administered via phone, mail, REDCap survey, video conference call and/or in person; ** These measures will be collected at T1, if participants did not complete them at prior T0 due to protocol change.

Table 1 b. ICAN MEASURES AND TIMELINE Caregivers			
	T1	T2	T3
FrsBE*	X		
IRI PT and EC (perspective taking and empathy (Aim 1)*	X	X	WLC only
CaGIC Aggression & Empathy/ Perspective Taking*		X	WLC only

Intervention (Intervention to Change Attributions that are Negative; ICAN). In a group therapy format (approximately 5 subjects per group), ICAN will train perspective taking through role-playing and *perspective-positioning* exercises.

Each of the 6 sessions will include the core exercises outlined in Table 2. See publication for more detail.²¹

A) Role Play Video Scenario

Participants will watch video scenarios depicting situations in which a character's motives are ambiguous (e.g., some-one bumped into you). After watching the scenario, participants will be asked to generate possible motives. In other words, produce as many potential explanations for the behavior²² After generating possible motives, they will be asked to role-play the scenario assuming a positive interpretation of the motive for the observed behavior. After the role-play, participants will be asked questions to process the experience and how the role play changed how they felt about the person's actions.

B) Perspective-Positioning Personal Experiences

Participants will be asked to produce personal examples of situations in which someone's behaviors led to an unpleasant outcome for the participant, and possibly perceived by the participant as purposeful. After introducing this scenario to the group, the participant will take part in a Perspective-positioning exercise in which participants will sit in one chair representing self-perspective (Chair A) to explore his/ her own thoughts and feelings surrounding the situation, and then move to a different Chair (Chair B) to experience the other person's perspective, eliciting their thoughts and feelings. After the Perspective-positioning activity, participants will be asked questions to help them process the experience and how it felt to "be" the other person and what they learned about the other person's feelings and motives for their actions, and how that in turn changed how they felt about the situation and the person's actions.

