Satisfaction Survey (CSQ8): To encourage honest feedback and ensure blinding of RA's, an unblinded RA will be responsible for collecting data on the CSQ-8 within approximately 1-2 weeks of completing the intervention (proximal to Time 2 for ICAN subjects and Time 3 for WLC subjects). In the case of withdrawal from treatment, the CSQ-8 may be conducted upon withdrawal from treatment, if the participant is agreeable. If participants withdraw, reasons for withdraw will attempt to be collected. At the end of the CSQ-8, the participant is presented with an optional comments section regarding their feedback and thoughts about what they liked/ did not like about the program.

Post-Treatment Qualitative Interview: To encourage honest feedback and ensure blinding of RA's, an unblinded RA will be responsible for administering the post-treatment Interview with the participant over the phone, via mail, email or in person within 1-2 weeks of completing treatment (proximal to Time 2 for ICAN subjects and Time 3 for WLC subjects).

Statistical Analysis Plan.

Primary Analyses. For Aim 1, the proportion of participants who complete at least 5 out of 6 sessions, and the proportion of participants who have satisfaction ratings that are average or higher on the standardized CSQ-8 will be calculated. For between group comparisons for Aims 2 and Aim 3, the primary analysis will be ANCOVA models with T2 measures as the outcomes, treatment group as the explanatory variable, and covariates of wave and T1 outcomes (except CaGIC which will not have T1 data since it is only collected at T2). Effect sizes (ω^2) will be calculated.

Secondary Analyses. WLC control outcomes at T2 will be compared to T1 for the ICAN and WLC group. If there are no significant differences, secondary analyses combining the data from the two treatment groups (assessments before and after intervention) will include ANCOVA, paired t-tests, and estimating effect sizes.

Missing Data. We will compare all baseline variables between subjects who drop out of the study to those who don't using two-sample *t* tests, chi-square tests or their non-parametric equivalents as appropriate. Also, we will collect as much information regarding reasons for missing data as possible. If we find that the missing data appear to be not at random, this important information will be used in designing the larger trial. Because of the small sample size, we will not attempt to model the missing data mechanism in this study.

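### The secondary analysis pools both arms' before/after data once a test on about 16 waitlist finishers is non-significant, and moderate untreated change will often pass that test

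*Combined protocol and SAP*

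**What the plan says.** The Secondary Analyses paragraph of the SAP first sets a comparison: "WLC control outcomes at T2 will be compared to T1 for the ICAN and WLC group". It then makes pooling depend on the result: "If there are no significant differences, secondary analyses combining the data from the two treatment groups (assessments before and after intervention"). The pooled work "will include ANCOVA, paired t-tests, and estimating effect sizes". The paragraph gives no significance level, equivalence margin or confidence-interval criterion, and does not say whether the decision is made outcome by outcome.

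The Sample Size Calculation section gives the numbers that bear on this test: "Thirty-two participants (16 per group) are expected to finish the study", and "16 subjects will provide 80% power to detect a difference in means of .78 standard deviations using a two-sided paired t-test".

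Table 1a schedules the "Buss Perry Aggression" questionnaire (AQ, the primary outcome) and the Epps stories at T0 and T2, with nothing at T1. For AIHQ and IRI the T1 entry is conditional: "These measures will be collected at T1, if participants did not complete them at prior T0 due to protocol change". These four instruments also decide eligibility at T0. For the AQ the criterion is: "Have above average aggression (>49 at telephone prescreening; >55 at T0 screening) on one of the Buss Perry Subscales".

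**The concern.** Failure to reject is treated as evidence that nothing changes without treatment. With about 16 pairs, the test misses moderate change more often than it finds it. Once it is passed, paired t-tests on the pooled arms have no control, so any drift, retest effect or regression to the mean counts as ICAN effect.

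Two features make this worse:

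- **Shared visit.** WLC T2 is both the end of the waiting period and the pre-treatment value for WLC. A T2 mean that is high by chance hides a fall during waiting and enlarges the T2-to-T3 fall that is then pooled.
- **Missing T1.** For AQ and Epps there is no T1 value to compare. For AQ, Epps and usually AIHQ and IRI, the ICAN pre-treatment value is the T0 score on which the person was selected, while the WLC pre-treatment value is T2. The two sets of pre-treatment values are not alike, and the ICAN set carries the regression to the mean.

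Aims 2 and 3 exist to give effect size estimates. A pooled estimate that appears to have been cleared by a test could be read as the treatment effect, although removing untreated change is what the waitlist arm is for.

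**Working it through.** **Inputs from the plan.** 16 finishers per arm; pre/post correlation 0.5; two-sided 0.05 (stated for the sample size, assumed here for the pooling test); AQ test-retest reliability .72 to .80. **Assumed.** Untreated drift of 0.2 to 0.5 SD of change, because the documents give no figure. At correlation 0.5 the SD of change is √(2 × (1 − 0.5)) = 1 outcome SD.

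**1. The plan's own figure.** Power of a paired t-test comes from the noncentral t with n − 1 df and noncentrality d√n. At n = 16 and d = 0.78 it is 83%; 80% is reached at d = 0.75. The stated .78 is slightly conservative and is accepted.

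**2. Chance of passing.** This is 1 − power. For n = 16, power at 0.2 / 0.3 / 0.4 / 0.5 SD is 0.116 / 0.203 / 0.322 / 0.465, so the pass rate is 88% / 80% / 68% / 54%. The largest observed shift that still passes is t(0.975, 15)/√16 = 0.53 SD. A non-significant result therefore does not rule out moderate change.

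**3. What follows a pass.** Simulation with zero ICAN effect, 16 per arm, three WLC visits and two ICAN visits, all correlations 0.5, 60,000 trials per setting. In each range, the lower figure has drift in the first interval only and the upper has it in both. The second pass column also requires WLC T2 not to differ from ICAN T1. The last two columns are given a pass on the WLC paired test.

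| Drift (SD of change) | Pass: WLC paired test | Pass: both comparisons | Pooled t-test falsely significant | Mean false effect (SD of change) |
|---|---|---|---|---|
| 0.2 | 88% | 82% | 9–21% | 0.11–0.22 |
| 0.3 | 80% | 72% | 14–41% | 0.17–0.33 |
| 0.4 | 68% | 58% | 23–65% | 0.23–0.44 |
| 0.5 | 54% | 43% | 34–85% | 0.29–0.55 |

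Adding the second comparison leaves the last two columns almost unchanged (14–41% at 0.3 SD). So does a correlation of 0.72 or 0.80, for the false-significance column under the WLC paired test.

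**4. Does the test remove bias?** At 0.3 SD, pooling with no test gives false significance in about 13% to 38% and a mean false effect of 0.15 to 0.31 SD. The test does not reduce this; conditional on passing, both rise slightly. The shared T2 explains it. With drift in both intervals, the mean raw pooled change among passing trials is 0.32 SD. The ICAN half is still 0.30, so the WLC half is 2 × 0.32 − 0.30 = 0.34 SD, above its true 0.30.

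**5. Regression to the mean on the AQ alone.** Assume score SD 10, source mean 50 to 55, correlation 0.5 between subscales, and selection on any of four subscales above 55. The expected fall in the total is (1 − r) times the selected group's excess over the source mean.

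- Source mean 50, r = .72: 0.28 × 5.9 ≈ 1.7 points, or 0.23 SD of change.
- Source mean 55, r = .80: 0.20 × 3.3 ≈ 0.7 points, or 0.11 SD of change.

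This arises in the first interval only and gives false significance of about 6% to 10%, against a nominal 5%.

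**The case against.** The strongest reply has four parts.

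- **The fault is the uncontrolled pooling, not the test.** Counting every trial rather than only those that pass, the test makes false pooled findings less frequent. At 0.3 SD the rates are 0.80 × 0.142 = 11% and 0.80 × 0.411 = 33%, against about 13% and 38% with no test. At 0.5 SD they are 0.535 × 0.337 = 18% and 0.535 × 0.851 = 46%, against 26% and 78%. This is correct. It does not make non-significance a valid reason to pool, and the estimates that do get reported are no less biased.
- **The drift is assumed, in a stable population.** Participants are at least a year post-injury, with stable medication and no current anger therapy. This stands as a limit on size. The upper figures need drift that recurs in the second interval, which regression to the mean at entry does not supply.
- **The sentence can be read otherwise.** It names both groups, its wording is plural, and up to 20 WLC participants could reach T2. With 20, pass rates at 0.3 / 0.4 / 0.5 SD are 75% / 60% / 43%. Requiring non-significance on every outcome would lower them further. The ambiguity is real, but none of these readings turns non-significance into evidence of no change.
- **The analysis is secondary.** The plan already makes the randomized T2 ANCOVA primary and attaches effect sizes to it. That limits the harm to the pooled results. The missing T1 values also touch the ANCOVA covariate, which is a separate matter.

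**Conclusion.** The concern holds. As written, a non-significant test on about 16 pairs licenses uncontrolled pooled analyses, and untreated change up to about half an SD passes more often than not under the WLC paired test. Change of 0.78 SD or more would usually be caught.

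The size of the resulting error depends on drift that the documents do not give. If regression to the mean on the AQ is the only source, the inflation is modest (about 6% to 10% false significance). At 0.3 SD of general drift it is 14% to 41% among trials that pass. These figures assume a 0.05 level, a decision made per outcome, 16 per arm and equal correlation between visits.

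Separately from any assumption about drift, the comparison cannot be carried out as written for AQ and Epps, nor for most AIHQ and IRI data. The primary randomized analysis is unaffected, so this should be corrected but does not threaten the main result.

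**What to change.** Delete the significance condition and replace the two sentences with:

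> For each outcome, the WLC change from the pre-randomization value (T1, or T0 where the measure is not collected at T1) to T2 will be reported with its 95% CI. Any before/after change or effect size pooled over both arms will be reported whatever that result, labelled descriptive and uncontrolled. The ICAN effect size will be taken from the randomized T2 comparison.

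If a model using T3 is added, the SAP should say that it gains from T3 only by assuming equal untreated change in both intervals. With a separate effect for each visit, T3 adds essentially nothing, because no untreated group remains at T3.

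An equivalence test is not a practical substitute. With true change zero, one-sided 0.05 and 80% power, it needs about 36 WLC finishers for a margin of ±0.5 SD and 97 for ±0.3 SD.

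The cost is SAP wording, with no new visits or data. The price is precision. At 16 per arm and correlation 0.5, the controlled estimate has SE √(0.75 × 2/16) = 0.31 outcome SD, against 1/√32 = 0.18 for the pooled paired analysis, so its interval is about 1.7 times as wide. Because the pooled figure would now always be reported, the label must appear wherever the figure does.
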